5.2.2 Duration of study activities

The study is anticipated to continue for approximately four weeks, excluding study enrollment period. In the event that additional studies are going to be conducted, new protocols will be developed specifically for those studies.

5.3 Patient Selection

The eligibility criteria for prospective enrollment of subjects are shown in **Table 1**.

Table 1. Inclusion/Exclusion Criteria for Enrollment of Subjects

Inclusion criteria	Female 18 years of age or older Documented symptoms of predominantly stress urinary incontinence as determined by the ICIQ questionnaire
Exclusion criteria	History of pelvic or lower back surgery Pregnancy or less than 12 months post partum History of physician-supervised PFMT History of Kegel exercises greater than once a month History of prior operative delivery Self-reported history of pelvic organ prolapse stage II or greater
Participant Withdrawal Criteria	Inability to demonstrate correct use of product Inability to devote sufficient time necessary to fulfill study goals Worsening of stress urinary incontinence symptoms

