Methodology Overview	
This will be a prospective cohort study of women > 18 years of age with symptoms of stress urinary incontinence, recruited via an online recruitment tool.
 
After screening, patients meeting inclusion criteria will be given a study brochure, and then given instructions on how to indicate desire to participate in the study. The patient will then be contacted for study participation, including explanation of study and details and completion of Informed Consent. Participants will then complete a pre-treatment urinary incontinence symptom questionnaire(ICIQ).
 
After completion of the above, the participants will then be given a Pelex Upp study, in addition to educational materials on use of the device, and a treatment schedule. Participants will perform a standardized biofeedback-mediated pelvic floor muscle training program with the study device 10 minutes a day, five times a week for 4 weeks. There will be a mid-study check in to assure all devices are functioning appropriately. At the end of the study, participants will complete a post-treatment urinary incontinence symptom questionnaire(ICIQ).
 
Endpoint of the study will be change in stress urinary incontinence symptoms as measured by the ICIQ. The ICIQ will be collected at 2 time points: before study entry, and at study close.

ABBREVIATIONS

PFMT	Pelvic floor muscle training
SUI	Stress urinary incontinence
OAB	Overactive bladder
UI	Urinary incontinence
PFM	Pelvic floor muscles
US/USA	United States of America

TABLE OF CONTENTS

1	INTRODUCTION	11
2	DESCRIPTION OF THE INVESTIGATIONAL PRODUCT	11
2.1	Overview	11
2.2	Proposed Intended Use Statement	11
3	STUDY OBJECTIVES	11
4	STUDY OVERVIEW	12
4.1	Study Approach	12
4.3	Study Duration.....	13
5	STUDY POPULATION	14
5.1	Sample Size and Target Study Population	14
5.1.1	Sample size	14
5.1.2	Study population	14
5.1.3	Alignment with intended study population.....	14
5.1.4	Alignment with intended use of the device.....	14
5.2	Recruitment Methods	14
5.2.1	Recruitment for Study	14
5.2.2	Duration of study activities.....	14
5.3	Patient Selection	15
6	STUDY MATERIALS	15
6.1	Investigational Product.....	15
6.1.1	Identity of the investigational product and accessories	15
6.1.2	Safety issues.....	16
6.1.3	Handling, storage, accountability.....	16
6.1.4	Required training.....	16
6.1.5	External studies.....	17
6.2	Other Study Materials	17
6.2.1	Materials to be provided by study site.....	17

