3 STUDY OBJECTIVES

The principal objective of this study is to demonstrate efficacy of the Pelex Upp in treatment of stress urinary incontinence. The secondary objective will be to determine ease of use of the Pelex Upp by patients at home.

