6.1.3 Handling, storage, accountability

The Sponsor will provide the Investigator with a supply of study devices for conduct of the study. All devices will be logged into the device accountability log. If a device is used in the investigation it will be documented in the device accountability log. Devices returned to the Sponsor will be noted as such in the device accountability log. A final accounting of devices will be being presented in the final clinical study report.

The Investigator shall permit an investigational device to be used only in subjects enrolled in the study. The Investigator shall not supply an investigational device to any person not authorized to receive it.

The Investigator or designee shall document receipt, use, and disposition of the device as it relates to:

- The quantity of the device, dates of receipt, catalogue and lot numbers;
- The names of all persons who received each device; and
- Why and how many units of the device have been returned to Sponsor or otherwise have left the possession of the Investigator.

The devices must be stored separately from other clinical supplies. Opened, unused devices must be returned to the Sponsor or destroyed on site as directed by the Sponsor.

The use of the study device outside of this protocol is prohibited. Each investigational site will identify a designee who will be held responsible for controlling the devices and ensuring that a device is dispensed only for the purposes of this study. This designee will be expected to retain all unused study supplies until the completion of the study and/or until a representative of the Sponsor has inventoried and made arrangements to return the supplies to the Sponsor. Upon completion or termination of this investigation or the Investigator's part of this investigation, or at the request of the Sponsor, the Investigator shall return any remaining supply of the device or otherwise dispose of the device as directed by the Sponsor.

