In the event that a subject revokes authorization to collect or use PHI, the Investigator, by regulation, retains the ability to use all information collected prior to the revocation of subject authorization. For subjects that have revoked authorization to collect or use PHI, attempts should be made to obtain permission to collect at least vital status (i.e., that the subject is alive) at the end of their scheduled study period.

The accountability procedure will consist of Pelex, Inc., the principal investigator and project team lead, respectively, being responsible for upkeep of the secured database and the only people with access, except for the IRB. The IRB will be allowed to access site, records, etc.

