8 DATA QUALITY ASSURANCE

The study screening questionnaire, pre-study survey, post-use survey, and post-study survey are all forms requiring input from subjects. Pelex will endeavor to use electronic forms of data capture whenever possible. Possible forms of electronic data capture include Google

forms and SurveyMonkey. These forms will be configured such that only [name] has access to the raw information in order to protect patient health information.

While obtaining the informed consent, [name] will ask the subject whether she is able to use electronic data forms. In the event that the subject indicates that she is unable to use electronic data forms, then the study team will include a paper journal in the study package. The study package will be returned to [name] who will be responsible for converting the paper form to an electronic format, anonymizing the electronic version, and archiving or destroying the paper form.

Beyond subject input, the study device are intended to collect physiological parameters and store this data on the device. The data will be salvaged when the study materials are returned to the study team. The device data will only be stored using the anonymous subject identifier. Data stored on the device hardware that is returned to the study team will be recovered by [name] following a protocol that has been established with the primary device manufacturer, Arduino. Anonymized recovered data will be collectively stored in a password protected data server or database. The raw data will be backed up at least once to local storage.

The data will be processed through reproducible measures, such as by writing start-to-finish code. When data processing is complete, this code will be applied to a copy of backed-up raw data to confirm the reproducibility of the analysis and integrity of the raw data.

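### The withdrawal criteria in 5.3 select on ease of use and on the symptom endpoint, and no visible text secures an exit assessment from the women withdrawn

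*Protocol*

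**What the plan says.** The eligibility table in Protocol 5.3 gives three participant withdrawal criteria: "Inability to demonstrate correct use of product", "Inability to devote sufficient time necessary to fulfill study goals" and "Worsening of stress urinary incontinence symptoms". They are worded as reasons to withdraw the participant, not as reasons to stop the device.

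Section 3 states: "The secondary objective will be to determine ease of use of the Pelex Upp by patients at home". The Synopsis (Methodology Overview) makes change in SUI symptoms on the ICIQ the endpoint and fixes its schedule: "The ICIQ will be collected at 2 time points: before study entry, and at study close".

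On completion of forms, the Synopsis says that participants fill in the closing ICIQ, 7.1 says that patients complete a tool before and after the study, and 7.2.1 calls for an eCRF for each enrolled subject. The materials list in 7.1 and section 8 also name a post-use and a post-study questionnaire. None of this text mentions a woman who has been withdrawn.

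The only data to be sought from an individual who leaves appear in 7.2.1, for a subject who revokes authorization to use her health information: "attempts should be made to obtain permission to collect at least vital status".

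**The concern.** Two of the three criteria are themselves study results. A woman who cannot use the device correctly is a negative finding for ease of use. A woman whose symptoms worsen is a negative finding on the endpoint. If either leaves before study close and is asked for nothing more, the missing answers are missing because they were unfavourable.

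Section 1 says that the study is meant to inform form factor, other design choices and patient feedback, and section 3 sets out to demonstrate efficacy. For both purposes these women are among the most informative. Section 9.3 plans to aggregate the questionnaire responses, and the aggregate can contain only what was collected. An analysis plan may later choose a denominator or a missing-data method, but it cannot supply a questionnaire that nobody requested.

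**Working it through.** The protocol states no withdrawal rate, effect size or power, so there is no figure to reproduce. The check is first textual, then a scale calculation on stated assumptions.

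**1. Does any visible text secure the answers?**

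- Synopsis: closing ICIQ from participants, tied to the end of the study. No time point at withdrawal.
- 7.1: pre- and post-study tool from patients. No rule after withdrawal.
- 7.2.1: an eCRF for each enrolled subject, with all requested data recorded. This covers withdrawn women as subjects, but does not say that an ICIQ is requested from them after withdrawal.
- 7.2.1: vital status only, and only after authorization is revoked.
- 7.4.2: forms completed as far as possible, but only when the whole study is discontinued.
- 13.2.1: fair treatment of women who withdraw. Nothing on data.

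The general duties could be read to include withdrawn women. None does so expressly.

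**2. What is likely to survive?** The device log records "Why and how many units of the device have been returned to Sponsor", and for device recordings section 8 says "The data will be salvaged when the study materials are returned to the study team". The fact of a failure may therefore be known. In the 7.1 materials list the post-use questionnaire is item 7, ahead of the initiation check-in (item 8), the mid-study check-in (item 9) and the post-study questionnaire (item 10). It may be answered before any withdrawal, but its timing is not visible. Most exposed are the closing ICIQ and the post-study answers.

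**3. Share of the sample.** Input: 5 subjects (Synopsis, 5.1.1). One loss is 1/5 = 20%; two are 2/5 = 40%.

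**4. How likely is a loss?** Let p be an assumed withdrawal probability per woman. The chance of at least one withdrawal is 1 − (1 − p)^5; the chance of at least two is 1 − (1 − p)^5 − 5p(1 − p)^4.

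| assumed p | at least one | at least two |
|---|---|---|
| 5% | 23% | 2% |
| 10% | 41% | 8% |
| 20% | 67% | 26% |
| 30% | 83% | 47% |

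**5. Direction for the ICIQ.** Let the women who remain have mean change m, and let each of k withdrawn women have change r × m. The mean over all five is m × [(5 − k) + k r]/5. The mean among those remaining, divided by the mean over all five, is therefore 5/[(5 − k) + k r].

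| r (assumed) | k = 1 | k = 2 |
|---|---|---|
| −0.5 | 5/3.5 = 1.43 | 5/2 = 2.50 |
| 0 | 5/4 = 1.25 | 5/3 = 1.67 |
| 0.5 | 5/4.5 = 1.11 | 5/4 = 1.25 |
| 1 | 5/5 = 1.00 | 5/5 = 1.00 |
| 1.5 | 5/5.5 = 0.91 | 5/6 = 0.83 |

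A ratio above 1 overstates improvement. For the worsening criterion, r is negative when the others improve on average, so overstatement is the expected direction. For the incorrect-use criterion r is open: 4.1 reports that pelvic floor training without biofeedback also helps, so such a woman could still improve.

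**The case against.** The strongest reply is that the forms are already required. Section 7.2.1 wants an eCRF for every enrolled subject, 12.2 makes the principal investigator responsible for completing all CRFs, and the closing ICIQ is described without exception. This stands in part: it would be wrong to say that the protocol imposes no form duty covering these women. But the eCRF content is not shown, and the closing ICIQ is tied to the end of the study, so the duty does not clearly reach a woman who has already left.

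Figure 1, the questionnaires and the consent form are not available here, and any of them could give timing or an exit procedure. The point is therefore limited to the visible text.

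Withdrawal for worsening protects the woman. That is right, and stopping the device gives the same protection. No interim symptom measure is described, either. If worsening is first seen on the closing ICIQ, nothing is lost.

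The study is an uncontrolled pilot of about 5, which 9.1 calls exploratory, and no test depends on the result. That lowers the stakes without removing them.

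Three stronger readings are tempting and not supported:

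- **Withdrawn women's data are discarded.** The protocol does not say so.
- **All their ease-of-use answers are lost.** The post-use questionnaire may come first, and the device log and recordings may show the failure.
- **Usability will be reported as 4/4 where 4/5 is true.** No such proportion is planned, and the difference is a choice of denominator, which can be left to the analysis plan.

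**Conclusion.** The point holds in limited form. Withdrawal under 5.3 selects on the secondary objective and on the endpoint, and no visible text expressly continues collection after withdrawal or sets an exit assessment. The closing ICIQ and any post-study ease-of-use answers of women with unfavourable results can be lost.

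Each loss is 20% of the planned sample. Beyond that the size is unknown: the withdrawal probabilities, the number withdrawn and the values of r above are all assumptions, and the resulting ratios run from 0.83 to 2.50. A reader might infer that the ICIQ improvement will certainly be overstated. The documents support that as the expected direction for the worsening criterion only. For incorrect use it is plausible but not certain. The link from the questionnaires to ease of use is a fair inference from their names and from section 1, since their content is not shown.

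**What to change.** In 5.3, recast all three criteria as reasons to stop using the device and not as reasons to leave the study. Add that a woman who stops is asked, at exit or at study close, for the existing ICIQ and post-study questionnaire, and for the post-use questionnaire if she has not yet completed it. Record which criterion applied. She remains free to decline or to leave the study altogether.

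The denominator for ease of use, and how inability or lack of time is scored, can be left to the analysis plan.

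The cost is two or three sentences and one or two form requests to each woman who stops early, with no new instrument or visit. The reported result may be less favourable.

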1 INTRODUCTION

Pelex, Inc. is a medical device company that is dedicated to addressing pelvic health disorders. The company is developing a non-invasive medical device that uses electromyography and neurostimulation to treat incontinence and other pelvic floor disorders. In support of its research and development efforts, Pelex is conducting a clinical study to assess the efficacy and usability of the electromyography component of the company's pelvic health product. Five patients suffering from stress urinary incontinence, a form of pelvic floor disorder, will be recruited to participate and the duration of participation is expected to be four weeks. The result of this study will be used to verify that the underlying technology functions as expected, identify subject preferences for device form factor and other design decisions, and capture other patient feedback.

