5.2 Recruitment Methods

5.2.1 Recruitment for Study

Eligible patients will be invited to participate in the study on a first-come, first-serve basis, subject to Pelex weekly recruitment goals. They will be informed of the possible risks of the procedure and will be required to give informed consent before study-specific procedures can proceed. A minimal financial inducement will not be offered, and subject recruitment materials will be used. Each subject will be informed that no personally relevant clinical information will be derived from the collected data, and that the only possible benefit to the subject is the improvement in their stress urinary incontinence. Medications will be documented. Each subject's involvement in the study will be limited to the period between signing of the informed consent form (ICF) and the end of the study, which is expected to be four weeks after study initiation.

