7 STUDY PROCEDURES

7.1 Workflow

The study design is a prospective cohort that enrolls adult female patients identified as having stress urinary incontinence via an online enrollment form to evaluate the effectiveness of the Pelex Upp in treatment of stress urinary incontinence. The treatment group will enroll 5 subjects. Following the granting of Informed Consent, subjects will be enrolled in the study within the prospective cohort and will complete a four-week course of biofeedback augmented PFMT using the Pelex Upp. Patients will complete a pre- and post-study urinary incontinence quality of life evaluation tool to assess response to the investigational device.

Subsequent treatment and work up will be dictated by the reported persistence of symptoms. Follow-up with care providers will be as needed, as determined by the patient.

[figure not shown]

Figure 1: Study Workflow

Item
1. Study Brochure
2. Prospective Subject Screening Questionnaire
3. Subject Consent Form
4. Instructional Materials
5. Study Package with Study Materials
6. Pre-Study Questionnaire
7. Post-Use Questionnaire
8. Study Initiation Check-in Communication
9. Mid-Study Check-in Communication
10. Post-Study Questionnaire
11. Thank You Communication

Table 1: Study Materials

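### Women who cannot use the device are withdrawn, although ease of use at home is the secondary objective, and no closing forms are asked of them

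*Protocol*

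**What the plan says.** Section 3 of the Protocol states: "The secondary objective will be to determine ease of use of the Pelex Upp by patients at home". The Introduction says the study is to "assess the efficacy and usability of the electromyography component" and that its results will inform form factor and other design decisions. Section 4.1 presents home use without invasive sensors or professionally placed electrodes as the product's advantage. Section 6.1.4 provides participants with instruction materials and describes no supervised training.

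Table 1 in section 5.3 has three rows: inclusion, exclusion and participant withdrawal. "Inability to demonstrate correct use of product" stands in the withdrawal row, so it applies to women already enrolled. The other two entries in that row are too little time for the study and worsening symptoms. The protocol does not say who judges correct use, or when.

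On the forms, the Synopsis says "The ICIQ will be collected at 2 time points: before study entry, and at study close". Section 8 says "The study screening questionnaire, pre-study survey, post-use survey, and post-study survey are all forms requiring input from subjects". The study materials list in section 7.1 includes a "Post-Use Questionnaire" and check-ins at initiation and mid-study. For a woman who revokes authorization to use her health information, section 7.2.1 says "attempts should be made to obtain permission to collect at least vital status" at the end of her scheduled period. Section 7.4.2 asks for forms to be completed as far as possible if the whole study is discontinued early.

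**The concern.** Being unable to use the product correctly is the most basic failure of ease of use. In a study of women working at home from written instructions, it is also the finding most useful for design. Table 1 treats it only as a reason for leaving. No provision says that the event counts as a result under the secondary objective, and none asks the woman for her closing forms.

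What is at stake is the secondary objective. If the rule is applied, the women who reach study close have been selected on ability to use the device, and their answers cannot show how usable it is for all who were enrolled. An analysis plan written later can choose a denominator. It cannot recover a survey that nobody asked the woman to complete.

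**Working it through.** The protocol states no figure to reproduce: section 9.1 calls the study exploratory and gives no sample size calculation. The check is therefore mainly a comparison of provisions, followed by a small illustration.

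**Which forms are asked of a woman withdrawn under Table 1?**

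| Provision | Where | Tied to individual withdrawal under Table 1? | Tied to the secondary objective? |
|---|---|---|---|
| ICIQ at entry and close | Synopsis | No; a withdrawn woman is not mentioned | No; it measures symptoms |
| Post-study survey | Sections 7.1, 8 | No | Not stated |
| Post-use survey | Sections 7.1, 8 | No; content and timing not shown | Not stated |
| Initiation and mid-study check-ins | Section 7.1 | No | Not stated; the Synopsis describes the mid-study check-in as a device-function check |
| eCRF for each enrolled subject | Section 7.2.1 | Covers her, but names no use-failure item | Not stated |
| Device data recovered on return | Section 8 | No | Not stated |
| Reason for device return | Section 6.1.3 | No; a device accountability record | No |
| Vital status at scheduled end | Section 7.2.1 | No; only after revoked authorization | No |
| Forms completed as far as possible | Section 7.4.2 | No; only if the study itself stops | No |

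No row requests the post-study survey or the closing ICIQ from a woman withdrawn under Table 1.

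**Illustration of the selection.** The input is n = 5 enrolled (sections 5.1.1 and 7.1). The number unable to use the device, k, is assumed, because the protocol gives no rate. Each woman is 1/5 = 20 percentage points. The share able among all enrolled is (5 − k)/5. Among those remaining it is (5 − k)/(5 − k) = 100% for any k below 5. Intervals are exact (Clopper-Pearson) 95%.

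| k (assumed) | Share of enrolled | Share of those remaining |
|---|---|---|
| 1 | 4/5 = 80% (28.4 to 99.5) | 4/4 = 100% (39.8 to 100) |
| 2 | 3/5 = 60% (14.7 to 94.7) | 3/3 = 100% (29.2 to 100) |

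**How often the rule would be triggered.** With an assumed per-woman failure rate p, and women independent, the chance of at least one failure among five is 1 − (1 − p)^5:

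- p = 5%: 1 − 0.95^5 = 0.226, or 23%
- p = 10%: 1 − 0.90^5 = 0.410, or 41%
- p = 20%: 1 − 0.80^5 = 0.672, or 67%

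**The case against.** The best defence is that Table 1 says when a woman leaves, not that her event goes unrecorded. Section 7.2.1 requires an eCRF for every enrolled subject, and a withdrawal with its reason is itself a record. The post-use survey, check-ins, stored device data and device-return log may each hold part of the story. In a listing of five women a withdrawal would be plain to see. This stands. A reader might infer that the failure is lost altogether, and the documents do not support that.

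It is also fair that ease of use is a matter of degree. Women who pass a demonstration can still find the device awkward at home, so the objective is not empty among those who remain. No share able to use the device is planned as an endpoint, and the choice of denominator may sit in an analysis plan that is not shown. The 80% against 100% contrast therefore cannot be read as an error in a planned result. The wide intervals overlap heavily, and no decision rule depends on them.

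Stopping a woman who cannot use a device correctly is ordinary practice, and nothing here argues against it.

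The defence does not reach two points. None of the possible traces is linked to withdrawal or to the secondary objective, and the closing forms are not asked of her. Both are matters of protocol conduct, not of analysis.

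**Conclusion.** The point holds in a limited form, as a change worth considering. As written, the withdrawal rule selects the women who give usability feedback at study close on the outcome the secondary objective is meant to assess. That feedback would come mainly from women already shown able to use the device, and no closing form is stated for those who were not.

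The size depends on how often the criterion is applied, which the documents do not let one estimate. Under assumed failure rates of 5% to 20%, the chance that it affects at least one of five women runs from 23% to 67%. The proportions show only how much one woman weighs in so small a group.

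A reader might also infer that the observed ICIQ change is biased. The documents give no basis for a direction or a size, and none is claimed. The conclusion rests on the readable protocol text; the content and timing of the post-use survey are not visible.

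**What to change.** In Table 1 of section 5.3, change the criterion from withdrawal from the study to stopping device training, and make the event a result. Suggested wording:

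> A woman unable to demonstrate correct use, as judged by [study-team role] at [named contact], may stop training. The event and its reason are recorded as a use failure under the secondary objective. Unless she withdraws consent, she is asked for the post-study survey and the ICIQ at study close.

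The sponsor chooses the role, the contact and the standard. Ask for the same two forms from women who stop for the other two reasons in that row, so that the closing data do not depend on why someone stopped.

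The cost is a short text change and one eCRF field; the forms are already listed. Section 5.2.1 says of every woman that her "involvement in the study will be limited to the period between signing of the informed consent form (ICF) and the end of the study", so asking at study close fits within the existing four weeks and adds no follow-up. Some women who stop may decline the closing forms, and that number should be reported.

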7.2.1 Collection of data

Source data is all information, original records of clinical findings, observations or other activities in a clinical trial necessary for the reconstruction and evaluation of the trial. Source data are contained in source documents. Examples of source documents in this study include medical records, memoranda, evaluation checklists, CRF worksheets, and Data Capture

An Electronic Data Capture (EDC) system using an electronic Case Report Form (eCRF) that is compliant with 21 CFR part 11 is the primary data collection instrument for the study. All data requested on the eCRF should be recorded. The EDC system will only allow for data to be collected based on specified fields. The EDC system also generates an audit trail for any corrected data. All data entered on an eCRF must be traceable to a source document.

eCRFs will be completed for each subject enrolled into the clinical study. The Investigator will review, approve, and electronically sign the completed eCRF for each subject; the Investigator's electronic signature will serve as a testament of the Investigator's responsibility for ensuring that all clinical data entered on the eCRFs are complete, accurate, and authentic.

Subjects will be identified in the EDC by a numeric code used for study purposes. Subjects are not identified by name. Data entry staff are expected to follow data protection practices. All procedures for the handling and analysis of data will be conducted using good computing practices meeting FDA guidelines for the handling and analysis of data for clinical trials.

Information about study subjects will be kept confidential and managed according to the requirements of the Health Insurance Portability and Accountability Act of 1996 (HIPAA). Those regulations require a signed subject authorization informing the subject of the following:

1. What protected health information (PHI) will be collected from subjects in this study;
2. Who will have access to that information and why;
3. Who will use or disclose that information; and
4. The rights of a research subject to revoke their authorization for use of their PHI.

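### Symptom worsening is a ground for withdrawal, but the protocol does not require the closing ICIQ from a withdrawn participant, so a probably unfavourable score could be lost (minor)

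*Protocol*

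**What the plan says.** The synopsis defines the endpoint as change in stress urinary incontinence symptoms on the ICIQ and fixes its timing: "The ICIQ will be collected at 2 time points: before study entry, and at study close". The only contact it describes between those points is about equipment: "There will be a mid-study check in to assure all devices are functioning appropriately".

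Table 1 in section 5.3 gives three participant withdrawal criteria. One is "Worsening of stress urinary incontinence symptoms". It comes with no threshold, instrument or assessment time.

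Section 9.3 pools the questionnaire responses. There is one treatment group of five (section 7.1) and no randomization (section 7.3). Section 9.1 calls the study exploratory, although section 3 states: "The principal objective of this study is to demonstrate efficacy of the Pelex Upp in treatment of stress urinary incontinence".

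**The concern.** The criterion that takes a participant out of the study is the bad direction of the quantity being measured. If withdrawal also ends data collection, whether a score is missing depends on the outcome itself. The scores most likely to be missing are those that count against the device, and no control arm is subject to the same loss.

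This cannot be left to a later analysis plan. Such a plan can choose an assumption for a missing closing score, but it cannot recover one that was never collected. No ICIQ is scheduled between entry and close that could stand in for it.

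**Working it through.** The plan has no figure of its own to reproduce: section 9.1 gives no sample-size calculation, and five is set by pilot status (section 5.1.1). The check is therefore a reading of the text, followed by an illustration of size under stated assumptions.

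**Text, side by side**

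- Synopsis: participants complete the post-treatment ICIQ at the end of the study. It neither restricts this to completers nor mentions withdrawn participants.
- Section 7.1: "Patients will complete a pre- and post-study urinary incontinence quality of life evaluation tool". Again general.
- Section 7.2.1: "eCRFs will be completed for each subject enrolled into the clinical study". This covers everyone enrolled, but does not say which forms a withdrawn participant completes.
- Section 7.2.1, on revoked authorization for health information: "attempts should be made to obtain permission to collect at least vital status". This is a different kind of leaver, and the stated minimum is not the ICIQ.
- Section 7.4.2: forms are completed as far as possible, but only when the whole study is discontinued.
- Section 13.2.1: covers how people who withdraw are treated, not their outcome data.

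None of these settles whether a participant withdrawn under Table 1 completes a closing ICIQ.

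**One participant lost.** Let d be her change and m the mean change of the other four. The mean of all five is (4m + d)/5 = m + (d − m)/5. Dropping her moves the mean by (d − m)/5. Assumed gaps of 2, 4 and 6 ICIQ points give 2/5 = 0.4, 4/5 = 0.8 and 6/5 = 1.2 points.

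**Average shift.** Assumptions, none from the protocol:

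- The final change D is N(μ, 1) in SD units, with negative values meaning improvement.
- An early signal S is N(μ, 1) and has correlation ρ with D.
- S > 0 counts as worsening.
- A fraction f of those with S > 0 is lost.

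Let p = P(S > 0) = Φ(μ). Then E[D | S > 0] = μ + ρφ(μ)/p, and the shift towards improvement is fρφ(μ)/(1 − fp).

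| μ | p | ρ | f = 0.10 | f = 0.25 |
|---|---|---|---|---|
| 0 | 0.500 | 1 | 0.042 | 0.114 |
| 0 | 0.500 | 0.5 | 0.021 | 0.057 |
| −0.5 | 0.309 | 1 | 0.036 | 0.095 |
| −0.5 | 0.309 | 0.5 | 0.018 | 0.048 |

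For example, with μ = 0, ρ = 1 and f = 0.10: 0.10 × 0.399/(1 − 0.05) = 0.042. The standard error of a mean of five is 1/√5 = 0.447 SD, so these shifts are about 4% to 25% of it.

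**Chance that at least one of five is lost**, 1 − (1 − fp)^5:

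- μ = 0: 1 − 0.95^5 = 0.226 (f = 0.10) and 1 − 0.875^5 = 0.487 (f = 0.25).
- μ = −0.5: 0.145 and 0.331.

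**Direction for one person.** With μ = 0, the probability that her final change is worse than the mean of the other four, given S > 0, is 1/2 + arcsin(ρ/√1.25)/π. This is about 85% at ρ = 1, 65% at ρ = 0.5 and 50% at ρ = 0.

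**Limiting case.** Suppose instead that every participant whose final change is worse than c SD is lost, with μ = 0. Those who remain show an apparent improvement of φ(c)/Φ(c). For c = 0, 0.5, 1.0 and 1.5 this is 0.80, 0.51, 0.29 and 0.14 SD. The chance of at least one loss among five is 97%, 84%, 58% and 29%.

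**The case against.** The strongest reply is that this is an omission, not a contradiction. A participant can meet a withdrawal criterion and still fill in the closing form. The general statements in the synopsis and in sections 7.1 and 7.2.1 can be read as covering everyone enrolled. Even for a participant who revokes authorization, the protocol foresees contact at the end of her scheduled period. The consent form attached under section 13.2, and Figure 1, are not available here and might address the point. The route to early withdrawal is also narrow. No ICIQ is scheduled before close and the check-in concerns device function, so worsening may first appear on the closing ICIQ, when the endpoint is already recorded. A post-use questionnaire is listed in section 7.1, but its content and timing are not given.

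Most of this stands, and it limits the severity. It does not remove the gap: no statement names withdrawn participants, and a criterion for participant withdrawal can just as naturally be read as ending participation altogether. A rule open to both readings should be settled before data are collected.

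A reader might infer something stronger: that the plan systematically removes unfavourable outcomes and so builds in a large false benefit, as in the limiting case. The documents do not support that. Nothing says that withdrawal ends data collection. Nothing provides for detecting every worsening before close, and no threshold for worsening is given.

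**Conclusion.** The gap is real and minor. Worsening is a ground for withdrawal, and no protocol text available here requires the closing ICIQ from a participant who has been withdrawn. The harm is conditional: someone must be withdrawn for worsening before close and no closing ICIQ obtained. The pooled change would then lose a probably unfavourable score out of about five. The direction is likely but not certain for one person, because someone worse mid-study need not end worse than the others.

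The size is unknown. At assumed losses of 10–25% of those who worsen, the average shift lies well below sampling noise; a single lost score can matter more to the reported mean. The loss fractions, correlations, normal distribution and point gaps are all assumptions. The exploratory purpose limits the stakes, although the principal objective is still worded as a demonstration of efficacy.

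**What to change.** Leave the withdrawal criteria unchanged. In the synopsis and in Table 1 of section 5.3, state that:

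- withdrawal does not end outcome collection;
- a withdrawn participant is asked, if she agrees, to complete the closing ICIQ at her scheduled four-week close;
- an ICIQ is also taken at withdrawal, as a fallback;
- each participant contributes one change score: the week-4 score if obtained, otherwise the withdrawal score, marked as early.

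Amend the synopsis sentence on two ICIQ time points to match. The week-4 form fits the period of involvement in section 5.2.1, which runs to "the end of the study, which is expected to be four weeks after study initiation".

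The cost is a few sentences and one or two short forms per withdrawn participant. A score taken at withdrawal is not fully comparable with week 4, and the reported result may look less favourable.
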